7.2 Secondary Efficacy Endpoints

7.2.1 Definitions

Secondary 1

Fraction of collected pupillometry data using native pupillogram.

For each of the measurements PLR, NC, and NY the measurements QC control will approve the measurements or not using the native pupillogram.

Secondary 2

Fraction of collected pupillometry data using refined pupillogram.

For each of the measurements PLR, NC, and NY the measurements QC control will approve the measurements or not using the refined pupillogram.

7.2.2 Analyses

Secondary 1

For each subject, the proportion of approved measurements over all measurements during visit 1 will be calculated for each of PLR, NC, NY, TR and Redness. The two light conditions will be analyzed separately for for PLR. The follow-up analyses will be analyzed separately and compared with the success rate at visit 1.

Secondary 2

For each subject, the proportion of approved refined measurements over all measurements during visit 1 will be calculated for each of PLR, NC, NY, TR and Redness.. The distribution over subjects in each drug class will be given with Mean, SD, median, minimum and maximum. The two light conditions will be analyzed separately. The follow-up analyses will be analyzed separately. and compared with the success rate at visit 1.

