Once completed, each video is automatically quality controlled. The evaluation of PLR, NC, and NY measurements rely on data where almost all videos need to be successfully converted to pupil size or iris position. The evaluation of motion patterns (tremor) relies on the position of the eye in collected images, and if too many consecutive images are missing the measurement is unusable. The color of the whites of the eye can be measured in any successful video during the PLR measurement if the led lamp is turned on, meaning it will always succeed if the PLR measurement succeeds. The subject will receive a notification if the measurement was performed successfully or not. The videos and the pupillometric variables will be transferred to the database for storage and to the external computer for further analysis.

In the external computer, key features (parameters that summarize different aspects of the collected raw data/pupillometric variables) will automatically be calculated from the pupillometric variables. As this is an early feasibility study, it is assumed that pupillometric variables will not be able to be processed for all videos with the current pre-defined mathematical models in PreVict Drugs.

During the update of the current mathematical and algorithm models, the data scientists at the software department at the sponsor will have access to the full videos that needs to be annotated. No other personnel at the sponsor will have access to this material.

Once the investigation is completed, the videos will be deleted and only a cut-out of the eye area from the videos will be transferred together with the pupillometric variables and key features to the R&D cloud where it will be stored. It is the stored data and results in the R&D cloud that will be used for continued product development after this clinical investigation.

The web-based careportal will in this investigation be used by the investigator or designee at a participating site for giving a subject access to the app. No other modules in the careportal will be used.

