10.3 Secondary Endpoint(s)

- The fraction of collected pupillometry data from the mobile phone application, which can be transformed into pre-defined key features using native pupillograms.
- The fraction of collected pupillometry data from the mobile phone application, which can be transformed into pre-defined key features using refined pupillograms and key feature extraction algorithms.

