8 CHANGES FROM THE CIP

No changes from the CIP are presented in this SAP except that missing data is added to the list of summary statistics.

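### The secondary success fractions have no defined unit or agreed number of measurements per visit, and tests with no recording drop out, so they can overstate whether pupillograms can be collected

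*SAP*

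**What the plan says.** **Endpoint and analysis.** Protocol (CIP) section 10.3 defines the first secondary endpoint as the fraction of collected data "which can be transformed into pre-defined key features using native pupillograms"; the second uses refined pupillograms and algorithms. SAP 7.2.1 labels the first endpoint "Fraction of collected pupillometry data using native pupillogram" and scores it by approval: "For each of the measurements PLR, NC, and NY the measurements QC control will approve the measurements or not using the native pupillogram". SAP 7.2.2 then states that "the proportion of approved measurements over all measurements during visit 1 will be calculated for each of PLR, NC, NY, TR and Redness". CIP 12.1 has the same QC-approval analysis, for PLR, NC and NY only.

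**Number of measurements.** CIP 10.5 plans two sets of four tests at each visit. The synopsis, CIP 10.8.1.2 and SAP 6.3 describe one series of four: one cross-eyes test (NC), one nystagmus test (NY) and two contraction tests (PLR), one per light condition.

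**Repeats and skipped tests.** SAP 6.4 has an unapproved measurement repeated, and CIP 6.9 allows one further try. If a test cannot be done, SAP 6.4 moves the subject on. The eCRF records performed and successful tests but not attempts per test. SAP 4.7 rules out imputation, and the FAS (SAP 4.2.2) requires one or more pupillometric measurements.

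**Tremor and redness.** SAP 7.2.2 adds TR (read here as tremor; the SAP's abbreviation list omits it) and Redness. CIP section 6 says of tremor that "if too many consecutive images are missing the measurement is unusable", and of eye colour that it depends on the PLR video, "meaning it will always succeed if the PLR measurement succeeds". SAP 8 states: "No changes from the CIP are presented in this SAP except that missing data is added to the list of summary statistics".

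**The concern.** The secondary objectives ask whether self-administered pupillometry can be used to collect pupillograms in people with substance use disorder. A subject who cannot complete a test is direct evidence on that question. The plan itself expects losses in processing: CIP section 6 notes that "it is assumed that pupillometric variables will not be able to be processed for all videos". A fraction based only on collected data captures failures among recordings but not tests that left no recording.

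The denominator is also open. Two analysts could follow SAP 7.2.2, one counting final results per test slot and the other counting attempts, and report different fractions from the same data. The conflict over one series or two sets leaves even the planned count per subject unsettled.

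**Working it through.** The plan states no expected success rate and no sample-size calculation, so there is no figure of its own to reproduce. The outcome mixes below are assumptions. The sample sizes, 30 and 15, are the ends of the range in CIP 10.6.4.

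**Step 1. Planned denominators per subject at visit 1.** With one series: NC 1, NY 1, PLR 1 per light condition. With two sets: NC 2, NY 2, PLR 2 per light condition. If each slot is counted once, the per-subject proportion can be 0 or 100% with one series, and 0, 50 or 100% with two sets. If attempts are counted, other values are possible.

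**Step 2. Effect of tests with no recording.** Take one NC slot per subject and at most one repeat (CIP 6.9). Let f = pass first time, r = pass on repeat, t = recorded but fail twice, u = not conducted and no recording, N = f + r + t + u.

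- Success over performed = (f + r)/(f + r + t)
- Success over scheduled = (f + r)/N
- Gap = (success over performed) × u/N, an exact identity, because (f + r + t)/N = 1 − u/N

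| Assumed f/r/t/u | N | Over performed | Over scheduled | Gap (points) |
|---|---|---|---|---|
| 26/2/1/1 | 30 | 28/29 = 96.6% | 28/30 = 93.3% | 0.966 × 1/30 = 3.2 |
| 18/6/3/3 | 30 | 24/27 = 88.9% | 24/30 = 80.0% | 0.889 × 3/30 = 8.9 |
| 12/6/6/6 | 30 | 18/24 = 75.0% | 18/30 = 60.0% | 0.750 × 6/30 = 15.0 |
| 13/1/0/1 | 15 | 14/14 = 100% | 14/15 = 93.3% | 1.000 × 1/15 = 6.7 |
| 9/3/1/2 | 15 | 12/13 = 92.3% | 12/15 = 80.0% | 0.923 × 2/15 = 12.3 |

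If the tests called not conducted were in fact recorded and failed after the repeat, they move from u to t. Then u = 0 and the gap is zero.

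**Step 3. Effect of counting attempts.** The mean per-subject proportion over attempts, among performed tests, is (f + 0.5r)/(f + r + t). At N = 30 this is 27/29 = 93.1%, 21/27 = 77.8% and 15/24 = 62.5%. These are 3.4, 11.1 and 12.5 points below success over performed. At N = 15 it is 13.5/14 = 96.4% and 10.5/13 = 80.8%, which are 3.6 and 11.5 points below.

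**Step 4. Numerator, side by side.** CIP 10.3 counts transformation into key features. CIP 12.1 and SAP 7.2 count QC approval on the native or refined pupillogram. CIP section 6 describes automatic QC of each video and, later, key-feature calculation on an external computer. No passage in either document equates approval with obtaining the key features.

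**Step 5. Tremor and redness.** The key features in CIP 10.8.3.1 are PLR 9 + NC 1 + NY 4 + tremor 8 + redness 1 = 23, which matches the protocol's total. Both additions therefore lie within the endpoint of CIP 10.3. What is missing is an approval definition in SAP 7.2.1 and an entry in SAP 8.

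**The case against.** The strongest reply is that this is a descriptive early-feasibility study with no hypothesis (CIP 9.4) and no pass/fail criterion (CIP 12.5). Skipped tests also remain visible elsewhere: in the eCRF record of performed and successful tests, the missing counts, the listing of patients outside the FAS, and the ability ratings in usability questions 6, 8 and 10. This stands as a limit on severity, since no error rate is affected. It does not settle what the fraction itself contains.

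Several stronger readings are tempting, and the documents do not support them:

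- *The SAP replaced the protocol's endpoint.* CIP 12.1 prescribes the same QC-approval analysis, so the tension is already inside the protocol. Approval on a refined pupillogram cannot be the on-phone check made at the visit, so it may be how the sponsor puts the key-feature endpoint into practice. The extraction documents cited in the protocol were not available to settle this.
- *There is no rule at all for tremor and redness.* CIP section 6 gives partial conditions: a tremor criterion without a threshold, and success for redness whenever PLR succeeds.
- *Every test that cannot be conducted vanishes from the fraction.* SAP 6.4 can be read as covering tests that still fail after a repeat. Those have recordings and would count as collected but not approved.
- *Per-subject values of 0 or 100% are an error.* Their mean is the ordinary sample proportion.
- *The scheduled fraction is what the plan already intends.* The endpoint wording refers to collected data, so a scheduled fraction is an addition beside it.

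**Conclusion.** The concern holds in a limited form, with moderate confidence. The denominator is undefined as to slot or attempt, and the protocol contradicts itself and the SAP on the number of measurements per visit. Tests with no recording, and subjects with no measurement, leave the fraction, which can then overstate whether pupillograms can be collected.

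The overstatement is success over performed tests times the share not conducted: 3.2, 8.9 or 15.0 points in the three assumed mixes at N = 30, and 6.7 or 12.3 points in the two at N = 15. These figures illustrate the mechanism and do not predict the result. The overstatement is zero if every failed test left a recording. The attempt-based differences in step 3 carry less weight: attempts are not in the eCRF, and the SAP does not say they will be counted from sponsor-held app output.

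The QC-versus-key-feature question and the approval rules for tremor and redness are points for clarification, not demonstrated errors. The matter should be fixed before analysis because these fractions are the whole secondary result.

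**What to change.** 1. Reconcile CIP 10.5 with the synopsis, CIP 10.8.1.2 and SAP 6.3 on the number of measurements per visit.
2. In SAP 7.2.2, define the unit as the test slot, scored on the final result after any repeat. Keep the fraction of collected data as the protocol endpoint. Beside it, report the fraction of scheduled measurements at visit 1, per measurement and per light condition for PLR, with tests not conducted counted as failures, for all eligible subjects who started testing. Name this group in SAP 4.2 as a supplementary set, because it goes beyond the FAS.
3. State whether QC approval on the native or refined pupillogram means that the pre-defined key features were obtained. If not, score key-feature success. CIP 10.8.3.1 sets NCdiff to 0 when the noise factor is 5 or less; that default should not count as success by itself.
4. Add approval rules for tremor and redness by citing the versioned extraction documents, since the tremor condition in CIP section 6 has no threshold. List the addition in SAP 8.

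**Cost.** SAP wording, reconciliation of the protocol passages, and minor programming. Performed and successful tests are already in the eCRF. Key-feature and refined-pupillogram success must come from app output held by the sponsor. The scheduled fraction will be equal to or lower than the fraction over performed tests.

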8.5 Risk Control

The potential risk for the subject during usage of Previct Drugs is assumed to be low or non-existing based on the identified potential adverse events listed above. Before the subjects will use Previct Drugs themselves, they will receive demonstration and training and will be under

	Clinical Investigation Code: KC09-108 Clinical Investigation Plan KCclin02	Revision: A
---	---	----------------

observation during usage of Previct Drugs as all measurements will be at the site. The site personnel will also assist as required during a measurement.

It should also be mentioned that as part of an investigation, the subjects will be well taken care of and monitored closely.

The reporting of adverse events related or unrelated to the device or procedure, and monitoring described in sections 13 and 19, respectively, will assure early detection of any increased risk or unanticipated subject safety concerns.

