9.5 Claims and Intended Performance of the Investigational Device

The following claims are suggested for Previct Drugs to collect preliminary evidence:

- Previct Drugs enables self-administered pupillometry using a commercially available smartphone.

The primary endpoint relates to the evaluation of specific usability questions about the usefulness of Previct Drugs through observation by the site personnel.

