10.8.1.2 Visit 1 (Baseline Visit)

Before any investigation-related procedures are initiated, the informed consent form (ICF) must be signed and dated by the subject and by the investigator who gave the subject the verbal and written information. The original ICF document will be retained in the Investigator Site File (ISF) and a copy provided to the subject. The investigator must obtain written informed consent from the subject before any clinical investigation-related procedures are performed, for further details on the informed consent process please see section 18.

After written informed consent has been obtained the subject is considered as enrolled. The subject will be allocated to the next available subject ID number, used for the identification of the subject in the investigation.

An enrolled subject will go through the screening parameters, e.g., relevant medical/surgical history, review of relevant current medication, and information on the subjects' demographics. ECG examination will be performed if the existing measurement is older than 2 years. The investigation also requires that a pregnancy test in fertile female subjects is analyzed. A breath test ~~urine~~ test will be performed for determine the drug

	Clinical Investigation Code: KC09-108 Clinical Investigation Plan KCclin02	Revision: A
---	---	----------------

content through LC/MS-MS analysis. Information on a subject's drug intake will be collected in the timeline follow-back of drugs and medicines last 24 hours.

After confirmation of the inclusion and exclusion criteria, the subject will be assessed as eligible. If the subject is not eligible, i.e., not fulfilling one of the inclusion criteria or fulfilling one of the exclusion criteria, the subject is to be seen as a screening failure and should be terminated from continuing in the investigation.

Previct Drugs measurement

The first test with PreVict Drugs will take place once the subject has been assessed as eligible. The site personnel will demonstrate for the subject how PreVict Drugs shall be used according to the IFU, and the procedures described in this CIP. The site personnel will assist as required during a test with PreVict Drugs. The subject will perform an eye measurement series which consists of four performed measurements:

- 1 Cross-eyes test
- 1 Nystagmus test
- 2 Contraction tests

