3.1.2 Secondary objectives

- Evaluate if self-administered pupillometry using a mobile phone application can be used to collect pupillograms for patients with substance use disorder.
- Evaluate if self-administered pupillometry using a mobile phone application, after refining the method for establishing pupillograms and key feature extraction algorithms, can be used to collect pupillograms from patients with substance use disorder.

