7.1 Primary efficacy endpoint

7.1.1 Definition

The analysis of the following 18 usability questions from the observation of a study subject during a test with PreVict Drugs.

1. Please evaluate the study subject's ability to use the mobile phone?
2. How did you perceive the study subject's ability to follow the instructions given by Previct Drugs?
3. If you experienced that the study subject had difficulties, please select the suitable choice/choices below.
4. How did the study subject experience to put him/herself in the right position to be able to start a test?
5. If you experienced that the study subject had any difficulty, please select the suitable choice/choices below.
6. How would you evaluate the study subject's ability to perform a Cross-eyes test?
7. If you experienced that the study subject had difficulties, please describe:
8. How would you evaluate the study subject's ability to perform a Nystagmus test?
9. If you experienced that the study subject had difficulties, please describe:
10. How would you evaluate the study subject's ability to perform a Contraction Test?
11. If you experienced that the study subject had difficulties, please describe:
12. How did the study subject experience keeping the phone still during the test?
13. If the study subject had difficulties, please select the suitable choice/choices below.
14. In addition to the basic instructions, did the study subject need additional support performing tests with Previct Drugs?

If No, please forward to question no. 17.

15. What type of additional support did the study subject need? Please select the suitable choice/choices below.
16. Was the study subject able to perform the test after receiving additional support?
17. How many efforts did it take the study subject to perform test with Previct Drugs?
18. How likely do you think it is that the study subject will be able to perform tests with Previct Drugs without assistance in a home environment?

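### The secondary fractions count approvals obtained with staff help, so they can overstate self-administered success; a cross-tabulation with usability question 14 would show it

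*SAP*

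**What the plan says.** The first secondary objective (SAP 3.1.2) is "Evaluate if self-administered pupillometry using a mobile phone application can be used to collect pupillograms for patients with substance use disorder". The second asks the same after the pupillograms and algorithms have been refined. Protocol 9.5 gives the claim for which preliminary evidence is sought: "Previct Drugs enables self-administered pupillometry using a commercially available smartphone".

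Staff help is part of the procedure. Protocol 10.8.1.2 states "The site personnel will assist as required during a test with PreVict Drugs", and Protocol 8.5 states "The site personnel will also assist as required during a measurement".

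SAP 7.2.1 makes quality-control approval the only condition for success. SAP 7.2.2 then states for Secondary 1 that "the proportion of approved measurements over all measurements during visit 1 will be calculated" for PLR, NC, NY, TR and Redness. Secondary 2 follows the same pattern.

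Support is recorded elsewhere. Usability question 14 (SAP 7.1.1) sets the basic instructions aside and asks "did the study subject need additional support performing tests with" the app. Question 15 asks what kind of support, and question 16 whether the test could then be done. SAP 7.1.2 gives each of these its own frequency table. SAP 4.10 plans no subgroups beyond light condition, and SAP 7.2.3 names treatment group, visit and, as an example of a further stratum, light condition.

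**The concern.** An approved measurement enters the numerator in the same way whether the subject managed alone or was helped through it. If help turns some failures into approvals, the fraction describes what subject and staff achieve together, while the objective and the claim are about what the subject achieves. Protocol 10.8.6 says it is not known how well subjects can perform a measurement and calls this an important usability question.

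The data that could separate the two situations are collected but stay in a different part of the report. No planned table shows how many subjects produced usable data without additional support. If that cross-tabulation is first made after the results are known, it will be post hoc.

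**Working it through.** The plan states no expected fraction, support rate or power, so there is no figure to reproduce. Every rate and count below is an assumption, used only to show how the quantities behave.

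**1. Gap between the planned fraction and what subjects would achieve alone.** For one measurement type, let s be the share of subjects helped, p_u the approval rate of those not helped, p_help the approval rate of those helped, and p_alone the rate the helped subjects would have had without help.

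- Planned fraction = (1 - s) × p_u + s × p_help
- Unaided fraction = (1 - s) × p_u + s × p_alone
- Gap = s × (p_help - p_alone)

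With p_u = p_help = 0.90 the planned fraction is 0.90 throughout. The gap in percentage points is:

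| s | p_alone 0.9 | 0.6 | 0.3 | 0 |
|---|---|---|---|---|
| 0 | 0 | 0 | 0 | 0 |
| 0.1 | 0 | 3 | 6 | 9 |
| 0.2 | 0 | 6 | 12 | 18 |
| 0.3 | 0 | 9 | 18 | 27 |
| 0.5 | 0 | 15 | 30 | 45 |

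The gap is zero if nobody is helped or if help leaves approval unchanged. It would be negative if help lowered approval.

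**2. What the report could show.** Take one measurement per subject and exact (Clopper-Pearson) 95% intervals. The documents give 15-30 subjects.

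| Quantity | N = 30, 10 supported | N = 15, 5 supported |
|---|---|---|
| Approved, overall | 27/30 = 90% (73.5-97.9) | 14/15 = 93% (68.1-99.8) |
| Approved, among those not supported | 18/20 = 90% (68.3-98.8) | 9/10 = 90% (55.5-99.7) |
| Approved and not supported, all subjects | 18/30 = 60% (40.6-77.3) | 9/15 = 60% (32.3-83.7) |

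The middle row shows why a split alone is not enough. Subjects who needed no support are selected for ability, so their rate can stay high however many others needed help. The bottom row keeps everyone in the denominator.

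**3. What separate tables can tell.** With A approved and S supported out of N, the number approved without support lies between max(0, A - S) and min(A, N - S). For A = 27, S = 10, N = 30 that is 17 to 20, or 57% to 67%. For A = 20 with the same S and N it is 10 to 20, or 33% to 67%. Separate tables therefore give a range, fairly narrow when approval is high and wide when it is not.

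**4. Why the bottom row is a lower bound.** Question 14 is answered for the observed test, not for each measurement. In the N = 30 example, 27 - 18 = 9 supported subjects were approved. Suppose each was helped with only one of PLR, NC and NY, spread evenly. Then 9/3 = 3 were helped on any one type, and 27 - 3 = 24 of 30 (80%) were approved without help on that type. The figure based on question 14 is still 60%.

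**The case against.** The strongest reply is that the endpoint is a technical yield. Protocol 10.3 defines it as the fraction of collected data that can be turned into key features, and for that purpose it does not matter who was prompted. This stands: as a yield the fraction is valid and should be kept.

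Second, unaided use is already covered by the primary endpoint. Questions 14 to 18 are all tabulated, question 18 asks about home use without assistance, and Protocol 9.5 follows its claim with a reference to the usability questions. This reduces the problem. It does not remove it, because those tables are not linked to whether usable data resulted.

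Third, Protocol section 6 calls the measurements self-administered and also allows staff to assist, so reading the word as meaning no support is one interpretation. That is fair. But question 18 and the home use described in Protocol 5.1 show that performance without help matters to the sponsor.

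Fourth, subject listings are promised (SAP 4.4 and 9) and the strata in SAP 7.2.3 are open-ended. These make the cross-tabulation possible but do not commit the plan to it.

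Finally, there is no hypothesis and no pass or fail criterion (Protocol 9.4 and 12.5), so no decision rule depends on the fraction. This stands and limits the weight of the point.

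A reader might go further and infer that the fractions are biased upward by a known or large amount, or that they are invalid. The documents do not support that. They give no support rate and no approval rates, and the upward direction assumes that help raises approval.

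**Conclusion.** The point holds in a limited form. The secondary fractions are valid as technical yield but mix assisted and unassisted approvals, so they can overstate what subjects achieve alone, which is the question the objectives and the Protocol 9.5 claim raise. Under the assumed ranges (10-50% supported, 90% approval with help, 0-60% alone) the gap is 3 to 45 points. The actual size cannot be obtained from the documents and may be zero.

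It would also be wrong to take approval combined with no support under question 14 as the true unassisted rate. It is a lower bound and may lie well below it. The overall fraction is an upper bound if help never lowers approval. Reporting both brackets the answer. This is an inexpensive improvement to a descriptive plan, not a flaw that undermines the study.

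**What to change.** In SAP 7.2.2, keep the overall fractions and state that they include assisted measurements. For Secondary 1 and Secondary 2 at visit 1, and for each measurement type (PLR by light condition, NC, NY, TR, Redness), add:

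- (a) the fraction split by question 14 (Yes/No);
- (b) the proportion of all FAS subjects with that measurement approved and question 14 answered No, labelled 'approved with no additional support at the visit (lower bound for unassisted success)'.

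State how (b) scores a measurement that was repeated after non-approval, since SAP 6.4 allows repeats and the eCRF does not hold attempts per test. Mention the split in SAP 4.10 and list the addition in SAP section 8.

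The cost is one descriptive table from data already collected, with no new visits, tests or subjects. There are two drawbacks. Because question 14 applies to the observed test or visit and not to each measurement, (b) may understate unassisted success materially. Cells will also be small at 15-30 subjects. Present both additions descriptively, beside the overall fraction as the upper bound if help never lowers approval.
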